6.2.1.1 Dose Reduction and Interruption

Table 6-15: INCB039110 Dose Modification for Toxicities

CTCAE Grade	Action and Dose Modification
Grade 1	
 Continue study treatment at same dose level (no dose modification). Monitor closely. Provide supportive care according to institutional standards.
Grade 2 (Tolerable)	
 Interrupt study treatment if clinically indicated. Monitor closely. Provide supportive care according to institutional standards. When toxicity resolves to grade 1 or baseline, restart study treatment at current dose level.
Grade 2 (Intolerable) Grade 3	
 Interrupt study treatment. Monitor closely. Provide supportive care according to institutional standards. When toxicity resolves to grade 1 or baseline, restart study treatment reduced by one dose level. If the grade 3 toxicity recurs, interrupt study treatment. When toxicity resolves to grade 1 or baseline, restart study treatment reduced by another dose level.
Grade 4	
 Interrupt study treatment. Monitor closely. Provide supportive care according to institutional standards. Restart with study treatment reduced by one dose level once toxicity resolves to grade 1 or baseline. If the grade 4 toxicity recurs permanently discontinue study treatment

7. ADVERSE EVENTS: LIST AND REPORTING REQUIREMENTS

Adverse event (AE) monitoring and reporting is a routine part of every clinical trial. The expected adverse events listed in the Investigator Drug Brochure and/or Package Insert and the characteristics of an observed AE (Section 7.1) will determine whether the event requires expedited reporting **in addition to** routine reporting.

The following definitions of terms apply to this section:

Adverse event means any untoward medical occurrence associated with the use of a drug in humans, whether or not considered drug related.

Life-threatening adverse event or *life-threatening suspected adverse reaction*. An adverse event or suspected adverse reaction is considered "life-threatening" if, in the view of either the investigator or sponsor, its occurrence places the patient or subject at immediate risk of death. It does not include an adverse event or suspected adverse reaction that, had it occurred in a more severe form, might have caused death.

Serious adverse event: An adverse event or suspected adverse reaction is considered "serious" if, in the view of either the investigator or sponsor, it results in any of the following outcomes:

- Death,
- a life-threatening adverse event,
- inpatient hospitalization or prolongation of existing hospitalization,
- a persistent or significant incapacity or substantial disruption of the ability to conduct normal life functions, or a congenital anomaly/birth defect.
- Important medical events that may not result in death, be life-threatening, or require hospitalization may be considered serious when, based upon appropriate medical judgment, they may jeopardize the patient or subject and may require medical or surgical intervention to prevent one of the outcomes listed in this definition. Examples of such medical events include allergic bronchospasm requiring intensive treatment in an emergency room or at home, blood dyscrasias or convulsions that do not result in inpatient hospitalization, or the development of drug dependency or drug abuse.

Suspected adverse reaction means any adverse event for which there is a reasonable possibility that the drug caused the adverse event. For the purposes of IND safety reporting, "reasonable possibility" means there is evidence to suggest a causal relationship between the drug and the adverse event. Suspected adverse reaction implies a lesser degree of certainty about causality than adverse reaction, which means any adverse event caused by a drug.

Unexpected adverse event or unexpected suspected adverse reaction. An adverse event or suspected adverse reaction is considered "unexpected" if it is not listed in the investigator brochure or is not listed at the specificity or severity that has been observed.

7.1 Adverse Event Characteristics

- **CTCAE term (AE description) and grade:** The descriptions and grading scales found in the revised NCI Common Terminology Criteria for Adverse Events (CTCAE) version 4.0 will be utilized for AE reporting. All appropriate treatment areas should have access to a copy of the CTCAE version 4.0. A copy of the CTCAE version 4.0 can be downloaded from the CTEP web site http://ctep.cancer.gov/protocolDevelopment/electronic_applications/ctc.htm.
- **For expedited reporting purposes only:**
 - AEs for the agent(s) that are listed in the Investigator Drug Brochure or package insert should be reported only if the adverse event varies in nature, intensity or frequency from the expected toxicity information which is provided.
- **Attribution of the AE:**
 - Definite – The AE is *clearly related* to the study treatment.
 - Probable – The AE is *likely related* to the study treatment.
 - Possible – The AE *may be related* to the study treatment.
 - Unlikely – The AE is *doubtfully related* to the study treatment.
 - Unrelated – The AE is *clearly NOT related* to the study treatment.

7.2 Expedited Adverse Event Reporting

Investigators **must** report to the Overall PI any serious adverse event (SAE) that occurs after the initial dose of study treatment, during treatment, or within 30 days of the last dose of treatment on the local institutional SAE form.

7.3 DF/HCC Expedited Reporting Guidelines

Investigative sites within DF/HCC will report AEs directly to the DFCI Office for Human Research Studies (OHRs) per the DFCI IRB reporting policy.

7.4 Expedited Reporting to the Food and Drug Administration (FDA)

The Overall PI, as study sponsor, will be responsible for all communications with the FDA. The Overall PI will report to the FDA, regardless of the site of occurrence, any serious adverse event that meets the FDA's criteria for expedited reporting following the reporting requirements and timelines set by the FDA.

7.5 Expedited Reporting to the company Supplying Drug (Incyte)

Incyte needs to be notified within 24 hrs of learning of an event. Incyte also needs to be provided a completed SAE form via email. SAE reporting for each subject begins the day the informed consent is signed by the patient and within 30 days after subject has completed or discontinued from the study or has taken last dose of the study drug, or as described in the IST protocol.

SAEs, occurring using Incyte Study drug, are reported in accordance with the effective protocol. SAEs occurring with any another commercial drug are reported to manufacturer of that drug in accordance with regulations and protocol.

Initial Serious Adverse events (SAEs) and/or subsequent follow-up reports should be reported via email to: ***[contact]***. SAE reports should be for a single subject with any additional documents (i.e. discharge summary, relevant test results) included for the same subject as individual attachments to the email. One email can have multiple attachments as long as each attachment contains relevant information for the same subject.

Please email your SAE form with a cover sheet and any additional attachments to the IST email address: ***[contact]***.

Tellex C3i is the PhV Clinical Research Organization (CRO) for Incyte. They will be contacting you for SAE follow-up requests and data clarifications by sending you a data clarification form (DCF). See follow-up section for details on this process. The following is general contact information for Tellex C3i.

TELERX C3I (Incyte PhV CRO)
US SAE [contact]

Tellex C3i tracks any critical outstanding follow-up items and questions and contacts the investigational site via a faxed DCF for the additional requested information until all outstanding queries are resolved. This includes requests for hospital discharge summaries, autopsy reports, and death certificates (if applicable), results of relevant laboratory, and diagnostic tests. The

investigational site faxes the additional information to Telerx C3i, using the Telerx C3i SAE fax number. The site personnel will update all relevant data on the appropriate SAE Report Form or equivalent to include any new or changed information. The Incyte Safety Representative (IC SR) will monitor outstanding queries and take appropriate action needed for resolution.

Any serious SAE upgraded to death or life-threatening requires that the follow up report be emailed to: ***[contact]*** email address within 24 hours of learning of the change.

If the SAE is not previously documented in the Investigator's Brochure for INCB039110 and is thought to be related to the study drug, a manufacturer's associate may urgently require further information from the Investigator or Sponsor for reporting to Health Authorities. Incyte will be notified within 24hrs of any IND safety event and will receive a copy of the initial and follow up IND Adverse Event reports within 48hrs of submission to regulatory authorities. This will be submitted to the following email address: ***[contact]***

Reporting of Pregnancy

An "Initial Pregnancy Report" or equivalent must be completed in full and emailed to ***[contact]*** within 24 hrs of discovery of a pregnancy of a subject who has taken the Incyte product or the pregnancy of a partner for a subject who has taken the Incyte product. The "Follow-up Pregnancy Report Form" or equivalent must be completed and emailed to ***[contact]*** within 30 days after delivery, so that Incyte is provided with information regarding the outcome of the pregnancy. If the pregnancy results in any events which meet the serious criteria (i.e., miscarriage or termination), the SAE reporting process needs to be followed and the timelines associated with an SAE should be followed.

7.6 Expedited Reporting to Hospital Risk Management

Participating investigators will report to their local Risk Management office any participant safety reports or sentinel events that require reporting according to institutional policy.

7.7 Routine Adverse Event Reporting

All Adverse Events **must** be reported in routine study data submissions to the Overall PI on the toxicity case report forms. **AEs reported through expedited processes (e.g., reported to the IRB, FDA, etc.) must also be reported in routine study data submissions.**

8. PHARMACEUTICAL INFORMATION

A list of the adverse events and potential risks associated with the investigational agents administered in this study can be found in Section 7.1

8.1 Dabrafenib mesylate (GSK2118436B) (NSC 763760)

Chemical Name: N-{3-[5-(2-Amino-4-pyrimidinyl)-2-(1,1-dimethylethyl)-1,3-thiazol-4-yl]-2-fluorophenyl}-2,6-difluorobenzene sulfonamide, methanesulfonate salt

Other Names: GSK2118436, GSK2118436A (free base)

Classification: BRAF inhibitor

CAS Registry Number: 1195768-06-9

Molecular Formula: C₂₃H₂₀F₃N₅O₂S₂ • CH₄O₃S

M.W.: 615.68 (mesylate salt)

Mode of Action: Dabrafenib mesylate (GSK2118436B) is a potent and selective BRAF kinase inhibitor. This inhibition suppresses downstream activity of pERK, a biomarker, and has antiproliferative activity against BRAF mutant tumors. The mode of action is consistent with ATP-competitive inhibition.

How Supplied: Dabrafenib mesylate (GSK2118436B) capsules are commercially supplied in bottles of #120 capsules as 50 mg and 75 mg capsules for oral administration.

- 50 mg capsules: Dark red capsule imprinted with 'GS TEW' and '50 mg'. Each bottle contains a silica gel desiccant.
- 75 mg capsules: Dark pink capsule imprinted with 'GS LHF' and '75 mg'. Each bottle contains a silica gel desiccant.

Storage: Store between 15°C to 30°C (59°F to 86°F).

Stability: Shelf-life studies of dabrafenib mesylate (GSK2118436B) are ongoing.

Route of Administration: Oral administration. Take dabrafenib mesylate (GSK2118436B) 1 hour prior or 2 hours after a meal. Pill cannot be crushed, chewed or dissolved in water.

Potential Drug Interactions: Dabrafenib mesylate (GSK2118436B) induces CYP3A4, 2C9, and possibly 2B6, 2C8, and 2C19 enzymes. Use caution in patients who are taking substrates that are metabolized in these enzyme pathways, such as warfarin.

Dabrafenib mesylate (GSK2118436B) metabolism appears to be mediated by CYP3A4 and CYP2C8. Use caution if strong inducers or inhibitors of CYP2C8 or 3A4 are co-administered with dabrafenib.

Dabrafenib solubility is pH-dependent and experiences decreased solubility at higher pH. Use caution in patients who are taking drugs that elevate gastric pH due to the theoretical risk of decreasing oral bioavailability of dabrafenib.

Patient Care Implications: In the case of overdose, patients should be treated symptomatically since there is no specific antidote. Hemodialysis is likely to be ineffective since dabrafenib mesylate is highly bound to plasma proteins.

Availability

Dabrafenib mesylate (GSK2118436B) is FDA-approved for the treatment of unresectable or metastatic BRAF-mutant melanoma. Commercial drug will be used in this study.

8.2 Trametinib dimethyl sulfoxide (GSK1120212B) (NSC 763093)

Chemical Name (IUPAC): equimolecular combination of N-(3-{3-cyclopropyl-5-[(2-fluoro-4-iodophenyl)amino]-6,8-dimethyl-2,4,7-trioxo-3,4,6,7-tetrahydropyrido[4,3-d]pyrimidin-1(2H)-yl}phenyl)acetamide with (methylsulfinyl)methane

Other Names: trametinib, GSK1120212, JTP-74057, JTP-78296, JTP-75303, Mekinist

CAS Registry Number: 1187431-43-1

Classification: MEK inhibitor

Molecular Formula: $C_{26}H_{23}FIN_5O_4 \cdot C_2H_6OS$

M.W.: 693.54 (dimethyl sulfoxide solvate), 615.41 (anhydrous parent)

Approximate Solubility: Trametinib dimethyl sulfoxide is almost insoluble in water (<0.0001 mg/mL at 25° C)

Mode of Action: Trametinib dimethyl sulfoxide is a reversible, highly selective, allosteric inhibitor of mitogen-activated extracellular signal regulated kinase 1 (MEK1) and MEK2. Tumor cells commonly have hyperactivated extracellular signal-related kinase (ERK) pathways in which MEK is a critical component. Trametinib dimethyl sulfoxide inhibits activation of MEK by RAF kinases and MEK kinases.

Description: Trametinib dimethyl sulfoxide is a white to almost white powder.

How Supplied: Trametinib is commercially supplied in bottles of #30 tablets, and is supplied as 0.5 mg and 2 mg (as free base) tablets.

- 0.5 mg tablets: Yellow, modified oval, biconvex, film-coated tablets with 'GS' debossed on one face and 'TFC' on the opposing face.
- 2 mg tablets: Pink, round, biconvex, film-coated tablets with 'GS' debossed on one face and 'HJM' on the opposing face.

Storage: Store tablets at 2°C - 8°C in the original bottle. Do not repack tablets or remove desiccant. Bottles should be protected from light and moisture.

Stability: Shelf life studies of trametinib dimethyl sulfoxide are ongoing.

Route of Administration: Oral. Take by mouth on an empty stomach, either 1 hour before or 2 hours after a meal. Pill cannot be crushed, chewed or dissolved in water.

Potential Drug Interactions

In vitro studies suggest that trametinib dimethyl sulfoxide is not a substrate of CYP enzymes or of human Pgp, BCRP, OATP1B1 or OATP1B3 transporters.

Trametinib dimethyl sulfoxide is a weak CYP2C8 inhibitor and weak CYP3A4 inducer. Drug-drug interactions with sensitive substrates of 2C8 and 3A4 are not anticipated.

Availability

Trametinib dimethyl sulfoxide (GSK1120212B) is FDA-approved for the treatment of unresectable or metastatic BRAF-mutant melanoma. Commercial drug will used in this study.

8.3 INCB039110

Chemical Name: 2-(3-(4-(7*H*-pyrrolo[2,3-*d*]pyrimidin-4-yl)-1*H*-pyrazol-1-yl)-1-(1-(3-fluoro-2-(trifluoromethyl)isonicotinoyl)piperidin-4-yl)azetidin-3-yl)acetonitrile adipate

Other Names: None

Classification: JAK inhibitor

CAS Registry Number:

Molecular Formula: C32H33F4N9O5

M.W.: 699.66

Mode of Action: INCB039110 is a potent and selective inhibitor of JAK1

How Supplied: INCB039110 will be provided as 100 mg (free-base equivalent) SR tablets. These tablets contain the active ingredient, hypromellose, microcrystalline cellulose, lactose monohydrate, and magnesium stearate. The higher strength tablet formulations (200 mg and 300 mg) also contain pregelatinized starch.

Storage: All INCB039110 drug product should be stored at ambient conditions (15°C to 30°C, or 59°F to 86°F).

Route of Administration: Oral administration. Pill cannot be crushed, chewed or dissolved in water.

Potential Drug Interactions: None identified

Patient Care Implications: In the case of overdose, patients should be treated symptomatically since there is no specific antidote. Hemodialysis is likely to be ineffective due to high binding to plasma proteins.

Availability: INCB039110 is an investigational agent and will be supplied by Incyte Pharmaceuticals.

9. BIOMARKER, CORRELATIVE, AND SPECIAL STUDIES

9.1 Biomarker Studies

9.1.1 Blood BRAF Assay

Collection of Specimens

Samples will be obtained via venipuncture at the time of safety lab collection. One 10 mL green top (heparinized) tube and 1 serum separator will be required to be collected at the following time points:

- Pretreatment
- Cycle 1, day 15
- Day 1 of every cycle of therapy
- At the time of progression

Handling of Specimens

Specimens will either be processed on site using the collection and processing SOP (Appendix H) or shipped to the [name] Laboratory overnight for processing and storage. Following processing, samples will be stored in a -80 degree freezer until batch analysis is performed.

Shipping of Specimens

Unprocessed specimens should be shipped overnight on wet ice (i.e. Freezer packs). Previously processed samples may be sent in batches on dry ice via overnight shipping. The address of the laboratory is:

[name] Laboratory
c/o [name]
[name]
[name]

Sites Performing Correlative Study

All DF/HCC study sites are expected to participate in this correlative study.

9.2 Pharmacokinetics

Little is known about the potential for drug-drug interactions (DDI) of the triple combination of dabrafenib, trametinib, and INCB039110. However, the available evidence regarding effect of each agent on cytochrome P450 isoenzymes and clearance of concomitantly administered drugs does not indicate a likely interaction.

Limited PK sampling will be performed in this protocol to enable analysis of trough levels of each agent pre-dose at the beginning of cycles 2, 4 and 6 in the case that the rate of combined toxicity is greater than expected.

Handling of Specimens

For each sample, the date and time of the dose and the date and time of the PK sample draw will be recorded and keep as Source Documentation in each individual patients chart.

INCB039110 PK Samples

1. At each time point, collect 4 mL whole blood PK sample into a properly labeled 4 mL

Lithium Heparin blood collection tube. Record the date and time each sample is collected. **Note the sampling time and volume of blood collection may differ with specific protocols and/or regimens.**

2. Immediately after collection, gently invert (do not shake) the evacuated blood collection tube for 30 seconds, then place on a standard roller for a minimum of 5 minutes. If a blood roller is not available, continue to invert the tube a further 8 – 10 times. Blood samples should be processed into plasma within 1 hour of sample collection
3. Centrifuge the tube at 1100 - 1500g for 10-15 minutes at 4-8° C within 1 hour of sample collection.
4. Immediately transfer plasma into two 2.0 mL Matrix TrackMate ScrewTop tubes, each containing approximately 0.75 mL of plasma.
5. Store at -20°C

Tissue analysis of pharmacodynamic effects

Collection of Specimens

Optional tumor biopsies will be performed pretreatment, one week (+/- 3 days) after commencing therapy with the combination as part of the phase I dose escalation and dose expansion cohorts, and post-treatment following completion of all study therapy. Biopsies may be also taken at any time, including at the time of clinically meaningful events such as response, disease progression or adverse events of interest. Only lesions that are deemed biopsiable through minimal risk procedures will be selected. For each biopsy, if possible, four core biopsy passes will be made. The first and third cores of tissue will be placed in formalin and then fixed in paraffin. The second and fourth cores of tissue will be flash frozen in liquid nitrogen and embedded in OCT. The first core will be used for IHC and primary outcome assessment. The second core will be used for gene and protein expression analysis. The third and fourth cores will be used to augment testing of cores 1 and 2, should the first and/or second cores be exhausted, and will be stored for future analysis.

Handling of Specimens

As described above, four cores will be obtained and fixed. The SOP for collection, handling, and processing is attached (Appendix H). Samples will either be stored at the individual DF/HCC sites and sent in batch at the time of planned correlative study analysis or sent to and stored at the [name] Laboratory at MGH. FFPE samples will be stored at room temperature. Frozen samples will be stored in a -80 degree freezer.

Shipping of Specimens

Samples may be sent at the time of collection or in batches via overnight shipping. Frozen samples should be sent on dry ice; paraffin blocks may be sent at room temperature conditions. One flash frozen sample will be sent on dry ice to [name] laboratory and the remainder of samples sent to [name] laboratory.

The addresses of the laboratories are:

Massachusetts General Hospital

Jackson 9
 [name]
 [name]

Site Performing Correlative Study: Being conducted only at Massachusetts General Hospital

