300 mg	8	1820 ± 780 1630	0.750 (0.500-2.00)	2.33 ± 0.665 2.26	4130 ± 1220 3950	4160 ± 1220 3980	143 ± 52.7 136	507 ± 359 443
500 mg	8	3750 ± 1230 3580	1.50 (0.500-3.00)	2.75 ± 1.32 2.57	9890 ± 3480 9330	9920 ± 3490 9360	103 ± 40.9 96.5	399 ± 202 358
1000 mg	8	7350 ± 3250 6770	1.50 (1.00-2.00)	9.81 ± 5.20 8.36	20500 ± 7010 19500	20700 ± 7000 19700	96.3 ± 32.0 91.7	1360 ± 886 1110
P-values from a 2-factor ANOVA of log-transformed data (factor = dose and subject)								
Dose		< 0.0001		0.319	< 0.0001	0.0008	< 0.0001	0.0003
Subject		0.0677		0.0342	0.0038	0.0938	0.0363	0.0069

ND = not determined because of large mean percentage AUC extrapolated (~43%) based on estimated t_{1/2} values, and as a result, statistical analysis for AUC_{0-∞} excluded the data from 10 mg dose.

Note: Values are mean ± SD and geometric mean, except that t_{max} is reported as median (range).

^a The terminal-phase t_{1/2} could not be determined in 3 subjects who received 10 mg dose because of low plasma exposures.

Drug-drug interactions

In vitro studies indicate that CYP3A4 is the major isozyme responsible for the metabolism of INCB039110 in human liver microsomes. In the human pregnane X receptor (hPXR) reporter gene assay, INCB039110 did not induce gene activity, suggesting that the potential for INCB039110 to induce CYP3A4 in clinical studies is low. In addition, INCB039110 did not significantly inhibit the activity of CYP1A2, CYP2B6, CYP2C8, CYP2C9, CYP2C19, CYP2D6, and CYP3A4, suggesting that the potential for INCB039110 to cause clinical drug-drug interactions through CYP inhibition is low.

Pharmacodynamic effect of INCB039110

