Fecal excretion was a major route of dabrafenib elimination in humans, accounting for 71.1% of the dose administered, and renal excretion accounted for about 20% of drug elimination.

Administration of dabrafenib with a high-fat, high-calorie meal reduced the oral bioavailability of dabrafenib when compared to the fasted state with a decrease in C_{max} and AUC of 51% and 31%, respectively, and delayed its absorption. Therefore, the current recommendation is to administer dabrafenib under fasting conditions, either 1 h before or 2 h after a meal.

Drug-drug interactions for dabrafenib:

Dabrafenib induces CYP3A4 and CYP2C9. Dabrafenib decreased the systemic exposures of midazolam (a CYP3A4 substrate), S-warfarin (a CYP2C9 substrate), and R-warfarin (a CYP3A4/CYP1A2 substrate). Co-administration of dabrafenib 150 mg twice daily for 15 days and a single dose of midazolam 3 mg (a CYP3A4 substrate) decreased midazolam AUC by 74%. Co-administration of dabrafenib 150 mg twice daily for 15 days and a single dose of warfarin 15 mg decreased the AUC of S-warfarin (a CYP2C9 substrate) by 37% and the AUC of R-warfarin (a CYP3A4/CYP1A2 substrate) by 33%.

In vitro studies show that dabrafenib is a substrate of CYP3A4 and CYP2C8 while hydroxy-dabrafenib and desmethyl-dabrafenib are CYP3A4 substrates. Co-administration of dabrafenib 75 mg twice daily and ketoconazole 400 mg once daily (a strong CYP3A4 inhibitor) for 4 days increased dabrafenib AUC by 71%, hydroxy-dabrafenib AUC by 82%, and desmethyl-dabrafenib AUC by 68%. Co-administration of dabrafenib 75 mg twice daily and gemfibrozil 600 mg twice daily (a strong CYP2C8 inhibitor) for 4 days increased dabrafenib AUC by 47%, with no change in the AUC of dabrafenib metabolites. Dabrafenib is a substrate of human P-glycoprotein (P-gp) and breast cancer resistance protein (BCRP) in vitro.

Pharmacodynamic effect of dabrafenib:

Median tumor pERK inhibition was 83.9% (range: 38.0 to 93.3%) in BRAF mutant melanoma subjects receiving doses of 70 to 200 mg BID. The relationship between exposure and % pERK inhibition was characterized using a maximum response (E_{max}) model with 100% maximum inhibition and IC_{50} of 134 ng/mL (95% CI: 92.7, 155) based on the sum of the potency-adjusted parent and active metabolite concentrations. A dose-related decrease in pERK was predicted with total daily doses <200 mg (100 mg BID) dabrafenib, with a plateau occurring beyond total daily doses of 200 mg thereafter.

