2.5 Correlative Studies Background

2.5.1 Pharmacokinetic Studies

While the pharmacokinetic data of single-agent INCB039110 and the combination of dabrafenib and trametinib are known, PK data of the triple combination have not been previously studied. The lack of evidence for drug-drug interactions with INCB039110 poses little risk that the clearance of dabrafenib and/or trametinib will be altered. We will collect trough samples on the first day of certain cycles in the protocol in order to measure drug concentrations of each agent if we encounter a rate of toxicity with the combination regimen that is higher than expected

The PK sampling regimen for this study is based on the following observations; steady state for trametinib was reached by approximately Day 15 and the C_{max} and AUC for dabrafenib at the RP2D are about 40% lower on Day 15 versus Day 8. In addition, accumulation of trametinib was observed in the combination study of trametinib and dabrafenib. Therefore, sampling of trough levels on day 1 of cycle 2 and cycle 4 and 6 will provide value that correspond to steady-state concentrations of dabrafenib and trametinib.

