5.4.2 Dabrafenib

Because there is a potential for interaction of dabrafenib with other concomitantly administered drugs through the cytochrome P450 system, the case report form must capture the concurrent use of all other drugs, over-the-counter medications, or alternative therapies. The Principal Investigator should be alerted if the patient is taking any agent known to affect or with the potential to affect selected CYP450 isoenzymes. Appendix B is a patient information sheet that can be used for this specific protocol and presented to the patient.

Dabrafenib mesylate is a substrate for CYP 3A4, 2C8, p-glycoprotein (Pgp), and breast carcinoma resistance protein (Bcrp). Strong inhibitors/inducers of these enzymes and transporters are prohibited for eligibility and during the study.

Mild or moderate inhibitors/inducers of CYP 3A4, 2C8, Pgp, and Bcrp should be used with caution as dabrafenib serum concentrations may be altered. Because the lists of these agents are constantly changing, it is important to regularly consult a frequently-updated list such as <http://medicine.iupui.edu/clinpharm/ddis/table.aspx>; medical reference texts such as the Physicians' Desk Reference may also provide this information.

Dabrafenib may induce CYP 3A4, 2B6, and possibly 2C8/9 and 2C19. Use concomitant medications that are substrates of these isoenzymes with caution as there may be loss of efficacy. Substitute with other medications that are not affected if possible.

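### Sections 9.2 and 8.3 discount an interaction that the protocol's own CYP3A4 data make plausible; the toxicity condition on trough analysis could leave low INCB039110 exposure unmeasured, and 13.3.1 promises PK parameters that trough samples cannot give

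*Combined protocol and SAP*

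**What the plan says.** Section 9.2 (Pharmacokinetics) opens by conceding that little is known about interactions of the triple combination. It then concludes that "the available evidence regarding effect of each agent on cytochrome P450 isoenzymes and clearance of concomitantly administered drugs does not indicate a likely interaction". Section 8.3 has the entry "Potential Drug Interactions: None identified" for INCB039110.

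The background sections give the facts on which such a conclusion should rest. Sections 2.2.3 and 5.4.3 report from in vitro work that "CYP3A4 is the major isozyme responsible for the metabolism of INCB039110 in human liver microsomes". Section 2.3.2 describes dabrafenib as a CYP3A4 inducer and reports that 150 mg twice daily for 15 days given with "a single dose of midazolam 3 mg (a CYP3A4 substrate) decreased midazolam AUC by 74" per cent. Section 5.4.2 warns about co-medications cleared by the enzymes that dabrafenib induces: "Use concomitant medications that are substrates of these isoenzymes with caution as there may be loss of efficacy".

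On sampling, section 2.5.1 argues that "The lack of evidence for drug-drug interactions with INCB039110 poses little risk that the clearance of dabrafenib and/or trametinib will be altered". It says trough samples will be collected to measure each drug "if we encounter a rate of toxicity with the combination regimen that is higher than expected", and 9.2 repeats that condition. The study calendar (footnote k) schedules pre-dose samples on Day 1 of Cycles 2, 4 and 6 for everyone. Section 1.1 makes describing the pharmacokinetics of all three drugs a secondary objective. Section 1.2 requires a full PK and safety review before the expansion cohort opens. Section 13.3.1 says that Cmax, two AUC measures and Tmax will be determined.

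**The concern.** Two things do not fit together.

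First, the protocol says that INCB039110 is mainly a CYP3A4 substrate in vitro and that dabrafenib induces CYP3A4, but never joins the two. Section 2.5.1 asks only whether dabrafenib or trametinib clearance might change. It does not ask whether INCB039110 is the drug affected, and the substrate warning in 5.4.2 is not applied to it.

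Second, the condition for looking at the troughs points the wrong way for this interaction. Induction would lower INCB039110 exposure, and lower exposure would not be expected to raise toxicity. If toxicity is as expected and the condition governs, the samples could stay in the freezer. The review before expansion could then take place with no scheduled INCB039110 concentrations. At stake is the interpretation of the expansion cohort: weak activity could reflect low exposure to the JAK1 inhibitor, and the trial would have no concentration data with which to consider that.

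A separate fault does not depend on CYP3A4: the parameters named in 13.3.1 do not match the sampling scheme.

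**Working it through.** The plan states no figure for the size of an interaction, so there is nothing to reproduce. The check sets the provisions side by side, with one illustrative calculation.

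**1. Is the interaction plausible on the protocol's own data?**
- Victim drug: CYP3A4 is the major isozyme for INCB039110 (2.2.3, 5.4.3; in vitro only).
- Inducer: dabrafenib 150 mg BID lowered midazolam AUC by 74% (2.3.2).
- Dose in this trial: Table 5.1 gives dabrafenib 150 mg BID at levels -1, 1, 2 and 3, that is, 4 of 5 levels.

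So it is plausible. No clinical data on INCB039110 with an inducer are given.

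**2. How large might it be?** The share of INCB039110 clearance that runs through CYP3A4 (call it fm) is not in the documents. It is an assumption here, varied from 0.25 to 1.0. If midazolam is taken as cleared wholly by CYP3A4, the fold induction is k = 1/(1 - 0.74) = 3.846, and the AUC ratio for INCB039110 is 1/(fm × k + 1 - fm).

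| Assumed fm | Denominator | AUC ratio | Fall |
|---|---|---|---|
| 0.25 | 0.962 + 0.75 = 1.712 | 0.584 | 42% |
| 0.50 | 1.923 + 0.50 = 2.423 | 0.413 | 59% |
| 0.75 | 2.885 + 0.25 = 3.135 | 0.319 | 68% |
| 1.00 | 3.846 | 0.260 | 74% |

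These figures show what the assumption implies. They are neither a forecast nor bounds.

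**3. Will the troughs be analysed?**

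| Provision | Toxicity condition? |
|---|---|
| 2.5.1, measuring concentrations | Yes |
| 9.2, trough analysis | Yes |
| 1.1, PK secondary objective | No |
| 1.2, PK review before expansion | No |
| 13.3.1, PK analysis | No |
| Section 10, calendar row titled PK Analysis | No |

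Nothing ranks these provisions. Footnote k, read alone, concerns collection and is compatible with either reading. Section 5, which lets PK analysis support an intermediate dose level, is permissive and does not settle the matter. The only other PK samples follow visual changes (6.1.14) or liver chemistry changes (6.1.16), so they too depend on adverse events.

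**4. Can the scheduled samples give the parameters in 13.3.1?** With 28-day cycles, Day 1 of Cycles 2, 4 and 6 falls on study days 29, 85 and 141. Each occasion yields one pre-dose sample. Cmax, Tmax and AUC over a dosing interval need several samples after a dose, so none of them can be determined.

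**The case against.** The strongest reply is that 9.2 is hedged and its condition is loosely worded. It says that little is known about the combination, and the toxicity phrase can be read as the reason for drawing samples, with no bar on analysing them otherwise. With 1.1, 1.2, 13.3.1 and the calendar row all unconditional, the team may well intend to assay everything. This stands in part. A reader might infer that the plan forbids analysis unless toxicity is raised; the documents do not support that. They support a conflict, or at best an ambiguity, that has to be resolved.

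A second reply is that assaying troughs would not show a fall. This also stands. INCB039110 starts together with the other two drugs, the first scheduled sample is at Cycle 2, and no reference trough is given. The only once-daily regimen in the multiple-dose healthy-subject study was 800 mg fed (2.2.3), against 100 to 400 mg on an empty stomach here (Table 5.1, 5.2.3).

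A third is that induction may be weaker than midazolam suggests, since dabrafenib lowered "the AUC of R-warfarin (a CYP3A4/CYP1A2 substrate) by 33" per cent. That substrate is cleared partly by another enzyme, so its smaller fall cannot be carried over to INCB039110. It does underline that the size is unknown.

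Finally, the planned tumour work on JAK1 and STAT proteins (2.5.2, 13.3.1) bears on target engagement. It is a partial substitute only: biopsies are optional (9.2) and do not measure drug concentration.

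**Conclusion.** The point holds as an inconsistency that should be fixed. The conclusion in 9.2 and the entry in 8.3 do not follow from the protocol's own CYP3A4 data, which make a fall in INCB039110 exposure plausible. The toxicity condition in 2.5.1 and 9.2 is poorly matched to that risk and is at odds with the unconditional PK provisions. If the condition governs, low exposure could go unmeasured before expansion. The mismatch between 13.3.1 and the sampling is certain and stands on its own.

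The size of any interaction is unknown. The illustrative 42% to 74% rests on assumed CYP3A4 shares of 25% to 100%, on midazolam-like induction, and on midazolam being cleared wholly by CYP3A4.

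A reader might infer that INCB039110 exposure will be substantially reduced, or that the MTD will be wrong. The documents support neither. The evidence for INCB039110 is in vitro with no stated clearance share, and the MTD is defined by toxicity of the three drugs as given together, whatever the exposure, so it is unaffected.

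**What to change.** 1. In 9.2, 2.5.1 and 8.3, state that dabrafenib may lower INCB039110 exposure through CYP3A4 induction and that the size is unknown.
2. Remove the toxicity condition from 2.5.1 and 9.2 so that they agree with 1.1, 1.2 and 13.3.1. Assay the scheduled INCB039110 troughs in all patients and summarise them by dose level and cycle. State that they describe exposure on the combination and cannot alone show a fall, because there is no pre-combination sample and no reference trough. Compare with single-agent data only if a comparable formulation, dose and food state can be found.
3. Use the Cycle 2 Day 1 troughs available at that time in the pre-expansion review in 1.2.
4. In 13.3.1, replace Cmax, AUC and Tmax with trough concentration.

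The cost is protocol wording plus INCB039110 assays: at most about 3 × 38 = 114, using the maximum of 38 evaluable patients in 13.2, plus any for replaced patients and fewer if patients stop early. No extra INCB039110 draws are needed. Cycle 2 assays must be run in time for the review. The documents give no assay price. No dose change is proposed.
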